10.9 Resistance Analyses

For all subjects in Arm A, full length NS3/4A or NS5A from baseline samples will be sequenced by next generation sequencing (NGS). Subjects in Arm B will have full length NS5B NGS performed on baseline samples only if they do not achieve SVR₁₂.

Subjects who do not achieve SVR₁₂ will have post-baseline resistance testing conducted if (1) they have on-treatment breakthrough; (2) if they have post-treatment relapse, with a study drug duration ≥ 77 days for subjects assigned to 12 weeks of treatment (Arm B) or study drug duration ≥ 52 days for subjects assigned to 8 weeks of treatment (Arm A); or (3) if they have HCV RNA \geq LLOQ at the end of treatment with at least 6 weeks of treatment. Subjects meeting one of these criteria will be referred to as subjects in the primary virologic failure (PVF) population, and a listing by subject that includes treatment arm, HCV subtype, prior HCV treatment experience, reason for SVR₁₂ non-response, time point(s) sequenced as closest to time of VF, and HCV RNA value at the VF time point(s) will be produced for these subjects. All listings described below will also display treatment arm, HCV subtype, prior HCV treatment experience, and reason for SVR₁₂ non-response in the subject identifier for each subject. A separate listing will delineate all subjects in the PVF population for whom no sequencing was performed (e.g., lost to follow-up while HCV RNA ≤ 1000 IU/mL).

Subjects treated with study drug who do not achieve SVR₁₂ and who do not meet the above criteria for the PVF population (e.g., those with less than 6 weeks of therapy who failed to suppress), but have a time point with HCV RNA \geq 1000 IU/mL after treatment discontinuation, will have the sample at that time point and the corresponding baseline sample sequenced. For subjects who are lost to follow-up with less than 6 weeks of therapy while not virally suppressed (e.g., HCV RNA never < LLOQ or have increase in viral load post nadir), the sample at the latest available time point with HCV RNA \geq 1000 IU/mL will be sequenced. These subjects will be referred to as the non-PVF population. A listing of all subjects in the non-PVF population with post-baseline sequencing available will be created that is similar to the listing of subjects in the PVF population with post baseline sequencing available.

For all subjects in Arm A, the region encoding full length NS3/4A and NS5A from their available baseline samples will be sequenced by next generation sequencing (NGS). For subjects in Arm A who do not achieve SVR₁₂, the region encoding full length NS3/4A and NS5A from their virologic failure/early discontinuation samples will be sequenced by NGS. For subjects in Arm B who do not achieve SVR₁₂, the region encoding full length NS5B from their baseline sample and the sample closest in time after VF with an HCV RNA level of \geq 1000 IU/mL will be sequenced by NGS.

For each DAA target, signature amino acid positions in genotype 2 are listed in [Table 8](#).

Table 8. List of Genotype-Specific Signature Amino Acid Positions and Associated Specific Variants

| GT2 Target | Signature Amino Acid Positions | Amino Acid Positions for Subgroup Variant Analysis |
|-------------------|---------------------------------------|---|
| NS3/4A | 36, 43, 54, 55, 56, 80, 155, 156, 168 | 155, 156, 168 |
| NS5A | 24, 28, 29, 30, 31, 32, 58, 92, 93 | 24, 28, 30, 92, 93 |
| NS5B | 159, 282 | |

An appropriate subtype specific prototypic reference sequence will be used for comparison with sequences from samples.

The following definitions will be used in the resistance analyses:

- Baseline variant: a variant present by NGS in a baseline sample ($\geq 2\%$ or $\geq 15\%$ prevalence within a subject's viral population depending on variant frequency threshold utilized) that was not present in the appropriate prototypic reference amino acid sequence for a given DAA target.
- Variant at signature amino acid position: variant (relative to reference) present in a baseline or a post-baseline sample at a signature amino acid position.
- Post-baseline variant: an amino acid variant in a post-baseline time point sample that was not detected at baseline ($< 2\%$) in the subject and is detectable in $\geq 2\%$ of the sequences from the sample.
- Enriched variant: a variant present at both baseline and in a post-baseline sample whose prevalence in the post-baseline sample is at least 20 percentage points greater than the prevalence in the baseline sample [(post-baseline % – baseline %) ≥ 20].
- Treatment-emergent variant: A post-baseline variant or an enriched variant.
- Variants emerging at an amino acid position: amino acid position where 2 or more subjects of the same HCV subtype have treatment emergent variants (with all variants at that position listed after the position).
Emergent variant: a treatment-emergent variant that is observed in 2 or more subjects of the same HCV subtype.

The following (Analyses 1, 2, and 3) will be available in the primary CSR:

Analysis 1: The following analyses will be performed for the arm described:

- The number and percentage of subjects in Arm A with baseline variants at detection-thresholds of 2% and 15% for variants at signature amino acid positions, and 15% for variants at non-signature positions. For analysis by signature amino acid positions, the number of subjects with variants at signature amino acid positions in NS3 only, NS5A only, NS3 + NS5A, any in NS3, any in NS5A, or any in [NS3 or NS5A] will also be provided.

- A listing of all baseline variants (2% detection threshold) at signature amino acid positions for each DAA target (NS3/4A and NS5A) for the ITT population of subjects in Arm A.
- A listing of all baseline variants (15% detection threshold) at non-signature amino acid positions for each DAA target (NS3/4A and NS5A) for the PVF population of subjects in Arm A.
- For subjects in Arm B who experience VF, a listing by subject of all baseline variants relative to prototypic reference sequence will be provided for NS5B.

Analysis 2: The impact of baseline variants on treatment outcome will be assessed for subjects in Arm A in the mITT-GT_VF population as follows: for each variant, the SVR₁₂ rate will be calculated for subjects with and without the variant and the 2 rates will be compared using Fisher's exact test. Analyses will be grouped by subject's HCV subtype and DAA target (NS3 or NS5A). Subjects not achieving SVR₁₂ due to non-virologic reasons will be excluded. These analyses will be performed for the following subgroups based on variants in NS3/4A and NS5A separately:

- Variants at signature amino acid positions (vs. no variant at that position), using detection thresholds of both 2% and 15%. The analysis will also summarize the number of subjects with variants in NS3 only, in NS5A only, any in NS3, any in NS5A, any in NS3 or NS5A, any in NS3 + NS5A.
- Variants at each non-signature amino acid position (vs. no variant at that position), at a detection threshold of 15%.
- Each variant at a signature amino acid position (vs. not that variant) using detection thresholds of 2% and 15%. The analysis will also summarize the number of subjects with variants in NS3 only, in NS5A only, any in NS3, any in NS5A, any in NS3 or NS5A, any in NS3 + NS5A.

Analysis 3: The following will be provided for subjects who do not achieve SVR₁₂ who have post-baseline resistance data available.

- Listings by subject of all treatment-emergent variants relative to the baseline amino acid sequence will be provided for each DAA target (NS3 and NS5A), separate listings for the PVF and non-PVF populations for subjects in Arm A.
- Listings by subject of all variants at signature amino acid positions in a post-baseline time point for each DAA target (NS3 and NS5A); with separate listings for those in the PVF and non-PVF populations for subjects in Arm A.
- Number and percentage of subjects in Arm A (with listing of subject numbers) with *variants emerging at an amino acid position*, with separate summaries for those in the PVF and non-PVF populations.
- Number and percentage of subjects in Arm A (with listing of subject numbers) with *emerged variants*, with separate summaries for those in the PVF and non-PVF populations.
- For subjects in Arm B who experience virologic failure who have post-baseline resistance data available, a listing by subject of all treatment-emergent variants relative to the baseline amino acid sequence will be provided for NS5B.

The following data will be available in the final CSR:

- Analysis 3 will be updated to include subjects who experience VF after Post-Treatment Week 12.
- The persistence of post-baseline variants at signature amino acid positions for each target (NS3 and NS5A) from subjects in Arm A who fail to achieve SVR₁₂ will be assessed at Post-Treatment Week 24. Listings by subject and time point of all treatment-emergent variants will be provided for each DAA target (NS3 and NS5A), separate listings for the PVF and non-PVF populations.

HCV Genotype/Subtype

Phylogenetic analysis will be conducted on HCV sequences from baseline samples from all subjects in order to accurately determine subtype.

Subjects' HCV genotype and subtype may be assessed based on the Inno-LiPA 2.0 Assay used by the Central lab (Covance), the HCV genotype determination by Sanger

sequencing of a region of NS5B by the Central lab (Covance) and/or from phylogenetic analysis of the full length NS3/4A and/or NS5A sequences performed by AbbVie. If the phylogenetic analysis is available, then it will be used to determine the subject's HCV genotype and subtype. If it is not available, then the Sanger sequencing assay result will be used to determine the subject's HCV genotype and subtype, if available. Finally, if neither the phylogenetic analysis result nor the Sanger sequencing assay results are available, then the Inno-LIPA assay results will be used to categorize the subject.

The above algorithm will be used to derive the final subtype used in summaries of efficacy subgroup analyses and resistance analyses.

The baseline characteristic summary will use the results from the central laboratory (Sanger sequencing or Inno-LiPA 2.0 Assay [if Sanger sequencing not available]).

A summary of HCV genotype and subtype as provided by the central laboratory (Sanger sequencing or Inno-LiPA 2.0 Assay [if Sanger sequencing not available]) versus phylogenetic analysis also will be provided.

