5.1.2 Modified Intent-to-Treat (mITT) Populations

Sensitivity analyses of the primary efficacy endpoint, when applicable, will be performed on two modified ITT populations below:

Modified ITT Genotype (mITT-GT) Population

mITT-GT population includes subjects in the ITT population excluding subjects with genotype other than HCV GT2 infection as determined in Section 10.9.

Modified ITT Genotype and Virologic Failure (mITT-GT-VF) Population

mITT-GT-VF includes all subjects in the ITT-GT population defined above, excluding subjects who did not achieve SVR₁₂ for reasons other than virologic failure.

Demographic analyses will also be performed on the mITT population(s), if needed.

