10.7 Efficacy Subgroup Analysis

Subgroup analyses will be performed for the primary efficacy endpoint of SVR₁₂.

Within each subgroup, the percentage of subjects with SVR₁₂ within each arm and the difference between treatment arms in the percentage of subjects with SVR₁₂ will be calculated, as will the corresponding two-sided 95% Wilson score intervals. A test of homogeneity will be conducted (Zelen's exact test) to evaluate whether differences between treatment arms are consistent across subgroups (i.e., confidence intervals for the difference in SVR₁₂ rates will not be compared to the non-inferiority margin).

Tests will be conducted at the nominal 0.05 level. The 2-sided 95% Wilson score confidence interval will be produced if there are at least 10 subjects in the subgroup.

The following subgroups will be analyzed:

- HCV genotype 2 subtype (final subtype as defined in Section 10.9);
- Prior HCV treatment history (naïve or IFN-experienced);
- IL28B genotype (CC or non-CC);
- Sex (male or female);
- Age (< 65 years, ≥ 65 – < 75 years, ≥ 75 years);
- BMI (< 25, or ≥ 25 kg/m²);
- Baseline HCV RNA level (< 100,000 IU/mL or ≥ 100,000 IU/mL;
< 800,000 IU/mL or ≥ 800,000 IU/mL; < 6,000,000 or ≥ 6,000,000 IU/mL;
< 10,000,000 IU/mL, or ≥ 10,000,000 IU/mL);
- Baseline fibrosis stage (F0 – F1, F2, F3, F4 (if applicable));
- Baseline platelet count (< 100 or ≥ 100 × 10⁹/L; < 150 or ≥ 150 × 10⁹/L);
- Baseline HOMA-IR (< 2 or ≥ 2 mU × mmol/L²) and (< 3 or
≥ 3 mU × mmol/L²);
- Baseline albumin (< 35 or ≥ 35 g/L);
- Baseline creatinine clearance (< 60, ≥ 60 to < 90, ≥ 90 mL/min);
- Baseline eGFR (< 30, ≥ 30 to < 60, ≥ 60 to < 90, ≥ 90 mL/min/1.73 m²);
- History of diabetes (yes/no);
- History of bleeding disorders (yes/no);
- History of depression or bipolar disorder (yes/no);
- History of cardiovascular disease (yes/no);
- Baseline metabolic syndrome (yes/no);
- Injection drug use (yes, within last 12 months; yes, more than 12 months ago;
or no);
- Presence of baseline resistance-associated variants (any NS3 variant [yes/no];
any NS5A variant [yes/no]; any NS3 and any NS5A [yes/no], any NS3 or any
NS5A [yes/no]) and (NS3 only, NS5A only, both NS3 and NS5A, or none);

- Concomitant use of Proton Pump Inhibitors (PPIs) (yes/no);
- DAA compliance (yes/no);
- Concomitant treatment with liver protectants (yes/no);
- Subject with high risk of carcinogenesis (Yes/No);
- Subject with advanced fibrosis (Yes/No).

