Subgroup analysis will also be performed on relevant combinations of subgroup variables if deemed clinically meaningful.

For the subgroup analyses, the presence of baseline resistance-associated variants as listed above are defined in Section 10.9.1.

All subgroup analyses will be performed for SVR₄ in the interim analysis except

- Presence of baseline resistance-associated variants (any NS3 variant [yes/no]; any NS5A variant [yes/no]; any NS3 and any NS5A [yes/no], any NS3 or any NS5A [yes/no]) and (NS3 only, NS5A only, both NS3 and NS5A, or none).

A logistic regression model will be used to explore the associations between each of the subgroup variables and SVR₁₂ by fitting a logistic regression model on all subjects in the mITT-GT-VF population. Among all candidate predictors, continuous measurements will be used where possible (e.g., continuous baseline log₁₀ HCV RNA level) in the logistic regression model. For the variables on presence of baseline resistance-associated variants, only one unique variable (NS3 only vs. NS5A only vs. both NS3 and NS5A vs. none) will be used in the logistic regression model. A stepwise logistic regression approach will be used to assess the strength of each subgroup variable in predicting SVR₁₂, with a significance level of 0.10 to enter and remain in the model.

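### NS3/NS5A variants are sequenced at baseline in Arm A only, so the between-arm variant subgroups and the pooled model term cannot be run as written, and the genotype/subtype rules conflict on who is typed by phylogeny

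*SAP*

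**What the plan says.** **Sequencing plan (SAP Section 10.9).** For Arm A: "For all subjects in Arm A, the region encoding full length NS3/4A and NS5A from their available baseline samples will be sequenced". For Arm B: "Subjects in Arm B will have full length NS5B NGS performed on baseline samples only if they do not achieve SVR₁₂". No NS3/4A or NS5A sequencing is described for Arm B.

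**Use of variant status (SAP Section 10.7).** Within each listed subgroup, the plan calls for SVR12 by arm, the between-arm difference with a Wilson interval, and Zelen's exact test of whether that difference is consistent across subgroups. The list includes "Presence of baseline resistance-associated variants (any NS3 variant [yes/no", followed by the NS5A and combined versions. The stepwise logistic model is specified "by fitting a logistic regression model on all subjects in the mITT-GT-VF population", with one four-level variable (NS3 only, NS5A only, both, none) among the candidates.

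**Genotype and subtype (SAP Section 10.9, HCV Genotype/Subtype).** The phylogenetic source is full-length NS3/4A and/or NS5A. It ranks first ("If the phylogenetic analysis is available, then it will be used to determine" genotype and subtype), then Sanger sequencing of an NS5B region, then Inno-LiPA. The same subsection says: "Phylogenetic analysis will be conducted on HCV sequences from baseline samples from all subjects". Section 7.1 lists phylogenetic subtype as a baseline characteristic without limiting it to Arm A.

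**Where the typing is used.** The mITT-GT population is formed by "excluding subjects with genotype other than HCV GT2 infection as determined in Section 10.9" (Section 5.1.2), and mITT-GT-VF is nested in it. Section 10.9 also assigns the hierarchy's result to the efficacy subgroup and resistance analyses.

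**The concern.** Two analyses in Section 10.7 need NS3/NS5A data from both arms, and the sequencing plan supplies them for one. Without an Arm B value there is no Arm B rate within a variant subgroup, no difference and nothing for Zelen's test to examine. In the pooled model, a programmer would have to decide how to treat 40 unsequenced subjects. The SAP gives no rule, so the choice could be made after outcomes are known.

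The genotype and subtype question is separate. If the sequencing plan is taken literally, the hierarchy types Arm A mainly by phylogeny and Arm B by Sanger or Inno-LiPA. Exclusion from mITT-GT could then rest on different assays in the two arms. If the statement about all subjects is taken literally, that need not happen. The text does not say which one governs.

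**Working it through.** The plan attaches no figure of its own to this point. The inputs are the planned allocation of 80 and 40 (Section 4.2) and the assumed SVR12 rates of 96% and 95% (Section 4.3).

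**1. Baseline data by arm under the sequencing plan**

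| | Arm A (80) | Arm B (40) |
|---|---|---|
| NS3/4A and NS5A | all with an available sample | none |
| NS5B by NGS | not planned | SVR12 non-responders only |
| Central-laboratory typing (Sanger, else Inno-LiPA) | available route | available route |

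**2. Variant subgroups.** The between-arm difference in a variant stratum is the Arm A rate minus the Arm B rate. The number of Arm B subjects with known status is 0 in every stratum, so the second term has no denominator. The difference, its Wilson interval and Zelen's test are undefined. This is an estimability problem, not one of precision.

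**3. Pooled logistic model.**
- Share with variant status missing by design: 40/120 = 33%.
- Expected SVR12 failures: 80 × 0.04 = 3.2 in Arm A and 40 × 0.05 = 2.0 in Arm B, 5.2 in total. In mITT-GT-VF there can only be as many or fewer, because non-virologic failures are removed.
- Complete-case fitting over the candidate set removes all of Arm B and 2.0/5.2 = 38% of expected failures. A four-level factor (3 parameters) then faces about 3 events.
- Coding unsequenced subjects as having no variant puts all of Arm B in that one level and leaves the other three levels to Arm A alone, so the variable is confounded with arm.

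Neither result is what Section 10.7 describes.

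**4. Is the restriction to Arm A stated elsewhere?** Section 10.9 limits the summaries and listings of baseline NS3/NS5A variants in Analysis 1, and all of Analysis 2, to Arm A. Section 10.7 drops the variant subgroups from the interim analysis only. Section 10.9.1 defines variant status for genotype 2 subjects with no arm limit. Nothing restricts the SVR12 variant subgroups or the model term.

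**5. Genotype and subtype, statements side by side.** (a) Phylogeny uses NS3/4A and/or NS5A. (b) Those regions are sequenced for Arm A only. (c) Phylogeny is done for all subjects, and Section 7.1 lists its result without an arm limit. Statements (a) and (b) together contradict (c). Using Arm B's NS5B sequences would not resolve this: they exist only for non-responders, so typing would depend on outcome.

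**6. Possible size in mITT-GT (illustration only).** The SAP gives no reclassification rate, so the counts are assumed: 77/80 versus 38/40, with the normal-approximation interval of Section 10.3.

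Lower bound = d − 1.96 × √[pA(1−pA)/nA + pB(1−pB)/nB]
= 0.0125 − 1.96 × √(0.9625 × 0.0375/80 + 0.95 × 0.05/40)
= 0.0125 − 1.96 × 0.0405 = −6.7%.

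| Arm A subjects reclassified as non-GT2 | Arm A | Difference | Lower bound |
|---|---|---|---|
| none | 77/80 | +1.3% | −6.7% |
| 1 failure | 77/79 | +2.5% | −5.1% |
| 2 failures | 77/78 | +3.7% | −3.5% |
| 3 failures | 77/77 | +5.0% | −1.8% |
| 1 success | 76/79 | +1.2% | −6.8% |
| 2 successes | 75/78 | +1.2% | −6.8% |

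Only reclassified failures move the bound noticeably, and nothing in the SAP shows that failures would be reclassified more often than successes.

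**The case against.** A reader might infer more: that genotype and subtype are definitely measured differently by arm, and that the mITT comparison and the subtype-adjusted model are therefore biased. The documents do not support that.

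- Sections 10.9 and 7.1 also contain text that gives phylogenetic typing to both arms. What is shown is a contradiction, not settled differential typing.
- The logistic sensitivity model in Section 10.6 names genotype 2 subtype as a covariate without naming its source. That is an ambiguity; bias there depends on which source is used.
- mITT-GT membership turns only on genotype 2 versus another genotype, Arm A typing at baseline does not depend on outcome, and no reclassification rate is given. A shift counted only from excluded Arm A failures would be one-sided.
- Section 10.9 promises a summary of central-laboratory against phylogenetic typing, which would show discordance where both exist.

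These objections stand, and they confine the second half of the point to a contradiction with a conditional consequence.

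It can also be said that the variant subgroups were surely meant for Arm A, that Analysis 2 already studies variant impact there with Fisher's exact test, and that the model is exploratory. This limits the damage and supplies the natural remedy. It does not make the Section 10.7 text executable: the restriction written for Analysis 2 is absent where the subgroups and the model are specified.

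**Conclusion.** The variant half is wrong as written. Given the sequencing plan in Section 10.9, NS3/NS5A status is absent for all 40 planned Arm B subjects (33% of the trial). The between-arm variant differences and Zelen's test are not estimable, and the pooled-model term either removes Arm B or is confounded with arm. This follows from the text; the expected failure counts rest additionally on the design rates of 96% and 95%.

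The genotype and subtype half is an internal contradiction that needs reconciling. If the sequencing plan governs, the hierarchy types the arms by different assays, with a possible effect on the mITT results whose size is unknown and probably small. If the all-subjects statement governs, the arms need not differ.

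The primary ITT analysis has no genotype exclusion and is unaffected. The reach is limited to sensitivity, subgroup, baseline and exploratory analyses.

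**What to change.** 1. **Section 10.7, subgroups:** present NS3/NS5A variant subgroups for Arm A only, with no between-arm difference and no Zelen test.
2. **Section 10.7, model:** remove the variant variable from the pooled stepwise model and leave variant impact to Analysis 2 in Section 10.9. Refitting the four-level term in Arm A alone would add little with about 3 expected failures.
3. **Sections 10.9 and 7.1:** reconcile the sequencing plan and the NS3/4A–NS5A basis of the phylogeny with the statement covering all subjects and the unrestricted baseline listing. If the sequencing plan governs, correct both to Arm A.
4. **Between-arm typing, in that case:** use the central-laboratory genotype and subtype (Sanger, else Inno-LiPA) in both arms for mITT-GT, mITT-GT-VF, the subtype covariate in Section 10.6 and the subtype subgroup in Section 10.7. Keep phylogenetic subtype for the Arm A resistance analyses. If sequencing of both arms is what is intended, state the Arm B regions and samples instead.

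Cost: SAP wording for items 1 to 4, since Section 10.9 already uses the central-laboratory results for the baseline summary. The downside is slightly less precise Arm A subtyping in comparative tables. The alternative in item 4 would need additional Arm B sequencing.
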